## GI Adverse Event Management Algorithm

Rule out non-inflammatory causes. If non-inflammatory cause is identified, treat accordingly and continue I-O therapy. Opiates/narcotics may mask symptoms of perforation. Infliximab should not be used in cases of perforation or sepsis.

[figure not shown]

Patients on IV steroids may be switched to an equivalent dose of oral corticosteroids (e.g. prednisone) at start of tapering or earlier, once sustained clinical improvement is observed. Lower bioavailability of oral corticosteroids should be taken into account when switching to the equivalent dose of oral corticosteroids.

28-Sep-2020

## Renal Adverse Event Management Algorithm

Rule out non-inflammatory causes. If non-inflammatory cause, treat accordingly and continue I-O therapy.

[figure not shown]

Patients on IV steroids may be switched to an equivalent dose of oral corticosteroids (e.g. prednisone) at start of tapering or earlier, once sustained clinical improvement is observed. Lower bioavailability of oral corticosteroids should be taken into account when switching to the equivalent dose of oral corticosteroids.

28-Sep-2020

## Pulmonary Adverse Event Management Algorithm

Rule out non-inflammatory causes. If non-inflammatory cause, treat accordingly and continue I-O therapy. Evaluate with imaging and pulmonary consultation.

[figure not shown]

Patients on IV steroids may be switched to an equivalent dose of oral corticosteroids (e.g. prednisone) at start of tapering or earlier, once sustained clinical improvement is observed. Lower bioavailability of oral corticosteroids should be taken into account when switching to the equivalent dose of oral corticosteroids

28-Sep-2020

## Hepatic Adverse Event Management Algorithm

Rule out non-inflammatory causes. If non-inflammatory cause, treat accordingly and continue I-O therapy. Consider imaging for obstruction.

[figure not shown]
Patients on IV steroids may be switched to an equivalent dose of oral corticosteroids (e.g. prednisone) at start of tapering or earlier, once sustained clinical improvement is observed. Lower bioavailability of oral corticosteroids should be taken into account when switching to the equivalent dose of oral corticosteroids.

\*The recommended starting dose for grade 4 hepatitis is 2 mg/kg/day methylprednisolone IV.

28-Sep-2020

## Endocrinopathy Adverse Event Management Algorithm

Rule out non-inflammatory causes. If non-inflammatory cause, treat accordingly and continue I-O therapy. Consider visual field testing, endocrinology consultation, and imaging.

[figure not shown]

Patients on IV steroids may be switched to an equivalent dose of oral corticosteroids (e.g. prednisone) at start of tapering or earlier, once sustained clinical improvement is observed. Lower bioavailability of oral corticosteroids should be taken into account when switching to the equivalent dose of oral corticosteroids.

28-Sep-2020

## Skin Adverse Event Management Algorithm

Rule out non-inflammatory causes. If non-inflammatory cause, treat accordingly and continue I-O therapy.

Patients on IV steroids may be switched to an equivalent dose of oral corticosteroids (e.g. prednisone) at start of tapering or earlier, once sustained clinical improvement is observed. Lower bioavailability of oral corticosteroids should be taken into account when switching to the equivalent dose of oral corticosteroids.

[figure not shown]
\* Refer to NCI CTCAE v4 for term-specific grading criteria.

^If SJS/TEN is suspected, withhold I-O therapy and refer patient for specialized care for assessment and treatment. If SJS or TEN is diagnosed, permanently discontinue I-O therapy.

28-Sep-2020

## Neurological Adverse Event Management Algorithm

[figure not shown]
Rule out non-inflammatory causes. If non-inflammatory cause, treat accordingly and continue I-O therapy.

Patients on IV steroids may be switched to an equivalent dose of oral corticosteroids (e.g. prednisone) at start of tapering or earlier, once sustained clinical improvement is observed. Lower bioavailability of oral corticosteroids should be taken into account when switching to the equivalent dose of oral corticosteroids.

28-Sep-2020

## Myocarditis Adverse Event Management Algorithm

Patients on IV steroids may be switched to an equivalent dose of oral corticosteroids (eg, prednisone) at start of tapering or earlier, once sustained clinical improvement is observed. Lower bioavailability of oral corticosteroids should be taken into account when switching to the equivalent dose of oral corticosteroids.

Prophylactic antibiotics should be considered in the setting of ongoing immunosuppression.

ATG = anti-thymocyte globulin; BNP = B-type natriuretic peptide; ECG = electrocardiogram; IV = intravenous; MRI = magnetic resonance imaging

28-Sep-2020

## APPENDIX 4 MSI STATUS TESTING

### TESTING PANEL DESCRIPTIONS (PCR AND IHC)

Bethesda method and Promega MSI Multiplex System (PCR) Panel Description and Classification of MSI Status

- Reference panel:
  - BAT25 (mononucleotide)
  - BAT26 (mononucleotide)
  - D5S346 (dinucleotide)
  - D2S123 (dinucleotide)
  - D17S250 (dinucleotide)
- Alternative loci:
  - BAT40
  - BAT34C4
  - TGF-□-RII
  - ACTC (635/636)
  - NR-21
  - NR-24
  - MONO-27
- Classification:
  - **If 5 loci tested (reference panel):**
    - ◆ MSI-H: ≥ 2 markers with instability
    - ◆ MSI-L: 1 marker with instability
    - ◆ MSS or MSI-L: 0 markers with instability
  - **If > 5 loci tested (reference panel plus alternative loci):**
    - ◆ MSI-H: ≥ 30-40% markers with instability
    - ◆ MSI-L: < 30-40% markers with instability
    - ◆ MSS or MSI-L: 0 marker with instability
  - **In the case of 1 PCR amplification failure:**
    - ◆ If ≥ 3 markers of 4 → MSI-H
    - ◆ If 1 marker of 4 → re-amplify

### **IHC method Panel Description and Classification of MSI Status Panel**

- hMSH2
- hMLH1
- hMSH6
- hPMS2

#### **Classification:**

- **MSI-H:** ≥1 markers with instability
- **MSS:** 0 marker with instability
- **MSI-L:** not evaluable with this technique

#### **Prioritization of Tumor Tissue Samples for MSI Testing**

- 1) Fresh biopsy (Preferred)
  - a) For MSI status confirmation
- 2) Archive tissue
  - a) For MSI status confirmation

If fresh biopsy cannot be obtained, archived tumor tissue prior to therapy is acceptable only if the archived tissue is the same tissue that was used for local MSI/MMR testing.

#### *Important Reminders:*

- Refer to Central Lab Flow Chart and protocol for specific sample requirements
- Central lab must confirm receipt of evaluable tumor tissue prior to vial assignment.
- Please contact BMS or The Central Lab if there are any questions

## **APPENDIX 5      WOMEN OF CHILDBEARING POTENTIAL DEFINITIONS AND METHODS OF CONTRACEPTION**

Appendix 5 provides general information and definitions related to Woman of Childbearing Potential and methods of contraception that can be applied to most clinical trials. For information specific to this study regarding acceptable contraception requirements for female and male participants, refer to [Section 3.3.1](#) of the protocol. Only the contraception methods as described in Section 3.3.1 are acceptable for this study.

### **DEFINITIONS**

#### **Woman of Childbearing Potential (WOCBP)**

A woman is considered fertile following menarche and until becoming post-menopausal unless permanently sterile. Permanent sterilization methods include hysterectomy, bilateral salpingectomy, and bilateral oophorectomy.

#### **Women in the following categories are not considered WOCBP**

- Premenarchal
- Premenopausal female with 1 of the following:
  - Documented hysterectomy
  - Documented bilateral salpingectomy
  - Documented bilateral oophorectomy

Note: Documentation can come from the site personnel's review of the participant's medical records, medical examination, or medical history interview.

- Postmenopausal female
  - A postmenopausal state is defined as 12 months of amenorrhea in a woman over age 45 years in the absence of other biological or physiological causes. In addition, females under the age of 55 years must have a serum follicle stimulating hormone, (FSH) level > 40 mIU/mL to confirm menopause.

Note: Females treated with hormone replacement therapy, (HRT) are likely to have artificially suppressed FSH levels and may require a washout period in order to obtain a physiologic FSH level. The duration of the washout period is a function of the type of HRT used. Suggested guidelines for the duration of the washout periods for HRT types are presented below. Investigators should use their judgement in checking serum FSH levels.

- 1 week minimum for vaginal hormonal products (rings, creams, gels)
- 4 week minimum for transdermal products
- 8 week minimum for oral products

Other parenteral products may require washout periods as long as 6 months. If the serum FSH level is > 40 mIU/ml at any time during the washout period, the woman can be considered postmenopausal.

## **CONTRACEPTION GUIDANCE FOR FEMALE PARTICIPANTS OF CHILD BEARING POTENTIAL**

End of relevant systemic exposure is the timepoint where the Investigational Medicinal Product (IMP) or any active major metabolites have decreased to a concentration that is no longer considered to be relevant for human teratogenicity or fetotoxicity. This should be evaluated in context of safety margins from the no-observed-adverse-effect level or the time required for 5 half-lives of the IMP to pass.

### **METHODS OF CONTRACEPTION**

Local laws and regulations may require use of alternative and/or additional contraception methods.

#### **Highly Effective Contraceptive Methods That Are User Dependent**

*Failure rate of <1% per year when used consistently and correctly.a*

- Combined (estrogen- and progestogen-containing) hormonal contraception associated with inhibition of ovulation and/or implantation (These methods of contraception cannot be used by WOCBP participants in studies where hormonal contraception is permitted by the study protocol)b
  - Oral (birth control pills)
  - Intravaginal (rings)
  - Transdermal
- Combined (estrogen-and progestogen-containing) hormonal contraception must begin at least 30 days prior to initiation of study therapy.
- Progestogen-only hormonal contraception associated with inhibition of ovulation (This method of contraception can only be used by WOCBP participants in studies where hormonal contraception is permitted by the study protocol)b
  - oral
  - injectable
- Progestogen-only hormonal contraception must begin at least 30 days prior to initiation of study therapy.

#### **Highly Effective Methods That Are User Independent**

- Implantable progestogen-only hormonal contraception associated with inhibition of ovulation and/or implantation (This method of contraception cannot be used by WOCBP participants in studies where hormonal contraception is permitted by the study protocol)b
- Intrauterine device
- Intrauterine hormone-releasing system (IUS) (This method of contraception cannot be used by WOCBP participants in studies where hormonal contraception is permitted by the study protocol)b,c

- Bilateral tubal occlusion

- Vasectomized partner

Having a vasectomized partner is a highly effective contraception method provided that the partner is the sole male sexual partner of the WOCBP and the absence of sperm has been confirmed. If not, an additional highly effective method of contraception should be used.

- Sexual abstinence

*Sexual abstinence is considered a highly effective method only if defined as refraining from heterosexual intercourse during the entire period of risk associated with the study treatment. The reliability of sexual abstinence needs to be evaluated in relation to the duration of the study and the preferred and usual lifestyle of the participant.*

- Continuous abstinence must begin at least 30 days prior to initiation of study therapy.
- It is not necessary to use any other method of contraception when complete abstinence is elected.
- WOCBP participants who choose complete abstinence must continue to have pregnancy tests, as specified in [Section 2](#).
- Acceptable alternate methods of highly effective contraception must be discussed in the event that the WOCBP participants chooses to forego complete abstinence
- Periodic abstinence (including, but not limited to, calendar, symptothermal, postovulation methods), withdrawal (coitus interruptus), spermicides only, and lactational amenorrhea method (LAM) are not acceptable methods of contraception for this study.

NOTES:

a Typical use failure rates may differ from failure rates when contraceptive methods are used consistently and correctly. Use should be consistent with local regulations regarding the use of contraceptive methods for participants in clinical studies.

b Hormonal contraception may be susceptible to interaction with the study treatment, which may reduce the efficacy of the contraceptive method. Hormonal contraception is permissible only when there is sufficient evidence that the IMP and other study medications will not alter hormonal exposures such that contraception would be ineffective or result in increased exposures that could be potentially hazardous. In this case, alternative methods of contraception should be utilized. For information specific to this study regarding permissibility of hormonal contraception, refer to Sections 6.1 INCLUSION CRITERIA and 7.7.1 PROHIBITED AND/OR RESTRICTED TREATMENTS of the protocol.

c IUSs are acceptable methods of contraception in the absence of definitive drug interaction studies when hormone exposures from intrauterine devices do not alter contraception effectiveness. For information specific to this study regarding permissibility of hormonal contraception, refer to [Sections 3.3.1 INCLUSION CRITERIA](#) and [3.4.1 PROHIBITED AND/OR RESTRICTED TREATMENTS](#) of the protocol..

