### **Study Population:**

Key inclusion criteria:

- Mainland Chinese participants (at least 18 years of age).
- ECOG 0-1
- Have progression or refractory disease
  - Arm A: solid tumor including but not limited to NSCLC, NPC;

- Arm B: solid tumor including but not limited to CRC MSI-H/dMMR;
- Arm C: solid tumor including but not limited to SCLC, GC and melanoma.
- Arm D: histologically confirmed recurrent or metastatic MSI-H/dMMR CRC;
- If a participant with following tumor types is enrolled, he/she can only be treated using one specific dosing schedule, e.g. NSCLC, SCCHN or mesothelioma patient is to be treated in Arm A only. SCLC patient is to be treated in Arm C only.
- For Part 1, failing at least 1 line of systemic therapy for advanced disease; OR, well documented refusal of participants to receive chemo or biological therapy.
- For Part 2, additional criteria must be met for inclusion:
  - Participants must have shown progression during, after, or have been intolerant to  $\geq$  1 line treatment(s) for metastatic disease, which must include at least a fluoropyrimidine, and oxaliplatin or irinotecan (participants who receive oxaliplatin in an adjuvant setting should have progressed during or within 6 months of completion of adjuvant therapy in order for oxaliplatin to count as a prior therapy needed for entry)
  - Participants willing to comply to provide tumor tissue (archival or fresh biopsy specimen), including possible pre-treatment biopsy
- Women of childbearing potential (WOCBP) must not be nursing or pregnant and must be using an acceptable method of contraception. WOCBP must have a negative pregnancy test within 24 hours prior to dosing with study drug.

**Study Drug:** includes both investigational [medicinal] products (IP/IMP) and non-investigational [medicinal] products (Non-IP/Non-IMP) as listed:

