## **3.3    *Study Population***

For entry into the study, the following criteria MUST be met prior to dosing on Day 1. No exceptions will be granted. As of 20-Dec-2021, enrollment into this study Part 2 was closed.

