### **3) Age and Reproductive Status**

Investigators shall counsel women of child-bearing potential (WOCBP) on the importance of pregnancy prevention, the implications of an unexpected pregnancy, and the potential of fetal toxicity occurring due to transmission of study drug to a developing fetus.

- a) Female Participants
  - i) Females ages 18 years, or age of majority, or older at time of consent
  - ii) Women who are not of childbearing potential are exempt from contraceptive requirements
  - iii) Women participants must have documented proof that they are not of childbearing potential.
  - iv) WOCBP must have a negative serum or urine pregnancy test (minimum sensitivity 25 IU/L or equivalent units of human chorionic gonadotropin) within 24 hours prior to the start of study treatment. An extension up to 72 hours prior to the start of study treatment is permissible in situations where results cannot be obtained within the standard 24-hour window.
  - v) Additional requirements for pregnancy testing during and after study intervention are located in [Section 5](#), Schedule of Assessments.
  - vi) The investigator is responsible for review of medical history, menstrual history, and recent sexual activity to decrease the risk for inclusion of a woman with an early undetected pregnancy
  - vii) WOCBP must agree to follow instructions for method(s) of contraception defined in [Appendix 5](#) and as described below and included in the ICF.
  - viii) WOCBP are permitted to use hormonal contraception methods (as described in [Appendix 5](#))
  - ix) A female participant is eligible to participate if she is not pregnant or breastfeeding, and at least one of the following conditions applies:

- (1) Is not a WOCBP
- OR
- (2) Is a WOCBP and using a contraceptive method that is highly effective (with a failure rate of < 1% per year), with low user dependency, as described in [Appendix 5](#) during the intervention period and for at least 5 months and agrees not to donate eggs (ova, oocytes) for the purpose of reproduction for the same time period
- b) Male Participants
  - i) Males, ages 18 years, or age of majority, or older at time of consent

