- o) All toxicities attributed to prior anti-cancer therapy other than alopecia and fatigue (which can be Grade 2) must have been resolved to  $\leq$  Grade 1, or returned to baseline, or stabilized before administration of study drug. Participants with toxicities attributed to prior anti-cancer therapy which are not expected to resolve to Grade 1 and result in long lasting sequelae, such as neuropathy after platinum based therapy, are permitted to enroll.
- p) Any serious or uncontrolled medical disorder that, in the opinion of the investigator, may increase the risk associated with study participation or study drug administration, impair the ability of the participant to receive protocol therapy, or interfere with the interpretation of study result.
- q) Women who are of childbearing potential or breastfeeding

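### Appendix 5 forbids three kinds of hormonal contraception on the very condition under which Section 3.3.1 permits them, and exclusion 2q bars the women those rules admit

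*Combined protocol and SAP*

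**What the plan says.** **Contraception.** Section 3.3.1, criterion 3 a) viii), states that "WOCBP are permitted to use hormonal contraception methods" and refers to Appendix 5. Criterion ix) (2) requires a highly effective method "with low user dependency, as described in" Appendix 5, during the intervention period and for at least 5 months. The opening of Appendix 5 calls its content general and adds: "Only the contraception methods as described in Section 3.3.1 are acceptable for this study".

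In the Appendix 5 list of user-independent methods, the implantable progestogen-only entry and the intrauterine hormone-releasing system (IUS) entry both carry the note "This method of contraception cannot be used by WOCBP participants in studies where hormonal contraception is permitted by the study protocol". In the user-dependent list, the combined hormonal entry has the same note in the plural. The progestogen-only entry beside it has the opposite note: usable only where hormonal contraception is permitted.

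**Eligibility.** Exclusion 2q in Section 3.3.2 reads "Women who are of childbearing potential or breastfeeding". Inclusion 3 a) iii) reads "Women participants must have documented proof that they are not of childbearing potential". Against these, the synopsis says that women of childbearing potential "must not be nursing or pregnant and must be using an acceptable method of contraception", and inclusion 3 a) iv) and ix) (2) set a negative pregnancy test and contraception as their conditions of entry.

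**The concern.** A site that works from the Appendix 5 list would tell a woman with an implant or hormonal IUS that her method is not allowed in this study. She might stop a method that the protocol elsewhere classes as highly effective, or be recorded as non-compliant although viii) and ix) (2) accept what she uses. Section 3.3.1 names fetal toxicity as the risk that these rules exist to prevent, so the instruction should not be wrong as written.

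The second conflict decides whether any such woman should be in the trial at all. One line excludes her and others set out how she may enter. No endpoint, estimate or analysis depends on either point; the issue is the safety instruction and the consistency of the eligibility text.

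**Working it through.** The plan gives no figure here to reproduce. The check is a count of methods and a comparison of text.

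**Step 1. Highly effective hormonal forms in Appendix 5, given that this protocol permits hormonal contraception.**

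| Entry | Forms | Group | Usable by its own note? |
|---|---|---|---|
| Combined hormonal (oral, vaginal ring, transdermal) | 3 | User dependent | No |
| Progestogen-only (oral, injectable) | 2 | User dependent | Yes |
| Implantable progestogen-only | 1 | User independent | No |
| Hormone-releasing IUS | 1 | User independent | No by the entry; footnote c calls it acceptable, with a condition |

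- Total: 3 + 2 + 1 + 1 = 7.
- Barred by the three notes: 3 + 1 + 1 = 5, leaving 7 − 5 = 2.
- If footnote c governs the IUS: barred 5 − 1 = 4, leaving 3.

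**Step 2. The user-independent list as a whole.** It holds the implant, intrauterine device, IUS, tubal occlusion, vasectomized partner and sexual abstinence: 6 methods. As written, 6 − 2 = 4 are usable (5 if footnote c governs). With the three notes corrected, all 6 are, and the implant and IUS meet ix) (2).

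**Step 3. Is the note inverted, or intended?** Three places in the same appendix point to inversion.

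- The progestogen-only oral and injectable entry makes permission the condition for use, which is the sensible direction.
- The less-than-highly-effective progestogen-only pill is barred where hormonal contraception is prohibited, which is the same rule in its negative form.
- Footnote c, attached to the IUS entry, describes these systems as acceptable.

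A rule that withdraws a hormonal method because hormonal methods are allowed has no evident purpose.

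**Step 4. Does Section 3.3.1 settle it?** Criteria vii), viii) and ix) (2) name no specific method. Each refers to Appendix 5. Appendix 5 refers back to Section 3.3.1. The reference is circular, and the list with the inverted notes is the only list a site has.

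**Step 5. Exclusion 2q against the rest.** Text that admits women of childbearing potential: inclusion 3 a) iv), vii), viii) and ix) (2); the synopsis; the screening pregnancy test in Table 5.1-1; testing every 4 weeks on treatment in Tables 5.1-2 to 5.1-4; tests at both follow-up visits in Tables 5.1-5 to 5.1-7; and site training on their enrollment in Section 9.1.3. Exclusion 2q contradicts all of these. The synopsis and ix) both pair pregnancy with nursing or breastfeeding, which suggests that 2q was meant to say pregnant.

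**Step 6. How long the contraception text can matter (upper bounds).** Assume the last first dose was given by 20-Dec-2021 and that the 5 months run from the last dose, which the text does not state.

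- Standard maximum: 20-Dec-2021 + 24 + 5 months = 20-May-2024, which is 637 days (20.9 months) after Amendment 07 of 22-Aug-2022.
- Late responder (response as late as month 24, then 12 more months): 20-Dec-2021 + 36 + 5 months = 20-May-2025, 1,002 days (32.9 months) after it.

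**The case against.** The strongest reply is that Appendix 5 presents itself as general text and gives precedence to Section 3.3.1, which plainly permits hormonal contraception. Footnote c also sends the reader to the inclusion criteria, so a careful site would not ban an IUS. That stands in part for the IUS. It does not cure the combined and implant entries, because Section 3.3.1 hands the choice of method back to Appendix 5.

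Second, the error is restrictive. Four user-independent methods remain, and ix) (2) still demands a highly effective method throughout, so the text never tells a woman to go unprotected. This stands and limits the severity.

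Third, inclusion 3 a) iii) follows the line exempting women who are not of childbearing potential and precedes the rules for those who are. It can fairly be read as asking for proof only from women claiming the exemption. On that reading it is loose drafting, and the true contradiction is with 2q alone.

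Fourth, a reader might infer from Section 3.3 ("No exceptions will be granted") that every treated woman of childbearing potential is an eligibility deviation. The documents do not support this. Deviation status depends on the protocol version in force when she enrolled. Amendment 06 (02-Jul-2021) edited inclusion criterion 3 and replaced Appendix 5, only 171 days before enrollment closed on 20-Dec-2021, and neither the previous wording nor the date 2q entered is shown.

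**Conclusion.** The contradiction is real. Three Appendix 5 notes reverse the rule they were meant to state and, read literally, bar 5 of 7 highly effective hormonal forms (4 of 7 if footnote c governs the IUS), including both user-independent ones. Exclusion 2q conflicts directly with the inclusion criteria, the synopsis and the test schedule.

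A reader might go further and conclude that none of the 7 forms is compliant. That needs a second rule: the remaining 2 fail only if *low user dependency* in ix) (2) means exactly the group headed as user independent, which is an inference. It also needs footnote c to carry no weight. The finding should not rest on it.

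The practical reach is small. Enrollment is closed, so what continues is the contraception instruction for any woman of childbearing potential still on treatment or within 5 months of it. The documents do not say how many of the 36 participants are in that position, and it may be none. No statistical result is affected. Correction is still worthwhile because this is a safety instruction in force and the change is trivial.

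**What to change.** 1. In Appendix 5, in the combined hormonal, implantable progestogen-only and IUS entries only, replace *cannot be used* with *can only be used*. This matches the progestogen-only entry already in the list.
2. Reword exclusion 2q to *Women who are pregnant or breastfeeding*.
3. Reword inclusion 3 a) iii) so that the proof is asked of women who claim not to be of childbearing potential.

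The first edit affects current conduct. The other two mainly make the text consistent, since later wording does not change the criteria in force when participants enrolled. If ix) (2) is meant to exclude user-dependent methods, the edit to the combined hormonal entry adds no usable method, but it removes the contradiction; whether those methods should count is for the sponsor to state.

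The cost is three entries and two eligibility lines. No visit, test or contact is added, so nothing works against Amendment 07's aim of reducing burden.
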